## Potential Risks related to Anesthesia

Risks associated with intravenous catheter placement include brief, local discomfort and possible bruising, which can occur at the site of the IV line. There is also a possible (rare) chance of infection, but every precaution will be taken to reduce this risk by keeping the IV site clean and dry. Risks associated with propofol administration include: pain at the site of injection, possible allergic reaction to the drug, depression of respiration which may necessitate placement of an endotracheal tube to assist breathing, and mechanical ventilation, or a decrease in blood pressure which may necessitate giving a drug or IV fluids to bring the subject's blood pressure up. These effects disappear when propofol is discontinued.

#### Justification for the Risks Involved

The risks of the proposed procedure are minimal, and the importance to mankind of the potential knowledge gains is substantial, making the risk/benefit ratio very low. We combine the state-of-the-art brain imaging facility currently in place in the University of Michigan Health System with the experience of the imaging staff and clinic anesthesiologists in the Department of Anesthesiology. These experiments will provide a unique opportunity to understand the neurophysiological mechanisms of anesthesia modulation of human consciousness. Therefore, we will provide a unique opportunity to expand our knowledge of anesthesia-modulated human consciousness.

## **Procedures for Minimizing Risks**

All research subjects will go through a screening process for inclusion and exclusion criteria performed by licensed physician. A licensed physician will be present at all MRI scanning sessions to monitor the subjects. When subjects express or exhibit anxiety regarding the scanner setting, they will be allowed to discuss these feelings. Attempts will be made to minimize the discomfort and anxiety. When in the scanner, subjects will be provided with a squeeze-ball alarm that will alert the scanner technician and the researcher that the subject desires to come out of the scanner. In such instances, the subject will immediately be removed from the scanner and appropriate measures will be taken to ensure his or her psychological health. Earplugs, demonstrated to reduce scanner noise to a non-damaging level, will be used to minimize hearing risks.

In addition, any other health problem that would be aggravated by an MRI scan will also be a cause for terminating the subject's participation. In the event of serious cardiac-respiratory problems or other medical emergencies, the hospital code team will be activated. Other medical problems will be treated by the monitoring physician. Any medical problems that arise after release, although unlikely, will be treated by a physician from the research team. All subjects will have to arrange transportation after the study, and agree to not drive, work, operate machinery, or make legal decisions for 24 hours after the study. Subjects will be informed of their right to withdraw from the study at any time.

A protocol has been established to handle unexpected medical emergencies arising in the scanner suite. This protocol deals with medical issues and the duties of each team member. This includes stopping the scanner, removing the patient and calling for outside medical assistance. All members of the research team participate in periodic emergency protocol drills in the scanner suite and a copy of the written protocol and protocol termination guidelines are present at all times. Subjects requiring intervention for any neurological or cardiovascular adverse event will be transferred to the Emergency Department for further evaluation and treatment as seen fit by the attending physician. More serious cardiac events such as ventricular tachycardia, ventricular fibrillation or any unstable rhythm will be immediately treated according to current Advanced Cardiovascular Life Support (ACLS) protocols. Research team physicians have immediate access to valium, diphenhydramine, epinephrine, lidocaine, and NTG for emergency use, in addition to a fully supplied and operational "crash cart" with EKG, defibrillator, suction, oxygen, and airway management equipment.

We plan to keep the LIFUP's intensity strictly under the FDA limit for diagnostic ultrasound (https://www.fda.gov/regulatory-information/search-fda-guidance-documents/marketing-clearance-diagnostic-ultrasound-systems-and-transducers). We will also perform a few pilot experiments to evaluate possible mild and moderate symptoms without the administration of propofol anesthetic.

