#### **LIFUP Method**

We will utilize the BrainSonix BXPulsar 1002 LIFUP System (BrainSonix Inc. http://www.brainsonix.com/). FDA has determined that our proposed clinical investigation is a nonsignificant risk (NSR) device study because it does not meet the definition of a significant risk (SR) device under 21 CFR 812.3(m) of the investigational device exemptions (IDE) regulation (21 CFR 812). An IDE application is not required to be submitted to, or approved by, FDA for a NSR study. This device contains a single-element, air-backed, spherical section ultrasound transducer with 61 mm diameter and 80 mm focal depth. The transducer is mounted in a plastic housing filled

with deionized, de-gassed water and sealed with a thin polyethylene membrane permeable to ultrasound. The transducer will be coupled to the scalp of the participant using a 3D-printed transducer holder that allows for sonication to occur in conjunction with ultrasonic standoff pads and ultrasound gel. The LIFUP system operates at a fundamental frequency of 650 kHz. Following the previous work [24,25], we plan to administer a pulse repetition frequency of 100 Hz and pulse width of 0.5 ms. A total of 30 sonications will be administered, with a derated spatial-peak temporal-average intensity (Ispta) of 720 mW/cm², each lasting 30 s, separated by 30 s pause intervals. Sonication will be administered in a 3 Tesla Philips scanner at University of Michigan Hospital. Using a rapid structural MRI sequence, the perpendicular will be adjusted along the apex of the transducer's concavity directly targeting a region of interest. We will utilize a neuronavigation system (Brainsight Navigation system, Brainbox Ltd, https://brainboxneuro.com/products/brainsight-tms-navigation) to ensure precise targeting and positioning of the transducer. At the target location, the estimated peak pressure will be 0.71 MPa, and the ultrasound beam width will be 5 mm. The estimated targeting accuracy (uncertainty) at the desired location is ±2.5 mm.

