The application of LIFUP over 0.5–5 min has been shown to produce persistent neuromodulatory effects, lasting from a few minutes to several hours. For example, excitation-like effects and changes in functional connectivity lasting for over an hour were reported in nonhuman primates and human subjects. Stimulation of the amygdala and supplementary motor area in nonhuman primates affected circuit connectivity, resulting in a change in coupling of fMRI activity between the LIFUP target and other brain areas [39,40]. LIFUP stimulation of the frontal eye field of macagues for 100 ms immediately before a visual cue shifted the bias of a choice task in favor of

the corresponding contralateral side [41]. The forgoing evidence supports the feasibility and potential effectiveness of LIFUP to modulate circuitry of interest.

LIFUP has been shown to be a safe and effective method to modulate human brain activity, when the stimulation parameters and protocol follow the available guidelines [38,42,43]. The majority of studies with ultrasound have reported no adverse events or evidence of anatomical damage [32,44–47]. Mild and moderate symptoms were reported such as neck pain, sleepiness, muscle twitches, itchiness, and headache [48,49]. An in-depth survey of the safety of ultrasound for human neuromodulation did not find any evidence of serious events in a large cohort of participants [50]. Specifically, 64/120 participants (53%) responded to follow-up questionnaire, and none of them experienced serious adverse effects. 7/64 reported mild to moderate symptoms (e.g., neck pain, problems with attention, muscle twitches and anxiety), that were perceived as 'possibly' or 'probably' related to participation in LIFUP experiments. The most common unrelated symptoms included sleepiness and neck pain. There were initial transient reports of mild neck pain, scalp tingling and headache that were extinguished upon follow-up. No new symptoms were reported upon follow up out to 1 month [50]. In addition, no studies have shown LIFUP induced tissue damage in the absence of heating, unless they utilized contrast agents to enhance cavitation effects [34]. Finally, the LIFUP appears to be safe even at intensities several times higher than the FDA limit for diagnostic ultrasound (720 mW/cm^2) [51].

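### The planned ultrasound intensity equals the limit that the plan promises to stay strictly under

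*Combined protocol and SAP*

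**What the plan says.** Three sections of the combined protocol and SAP bear on this.

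- LIFUP Method sets the exposure: 30 sonications "with a derated spatial-peak temporal-average intensity (Ispta) of 720 mW/cm²", each of 30 s, with 30 s pauses. It also says "we plan to administer a pulse repetition frequency of 100 Hz and pulse width of 0.5 ms", and that at the target "the estimated peak pressure will be 0.71 MPa".
- Human Studies and Safety Profile related to LIFUP gives the only number for the regulatory limit. In summarising the literature it says LIFUP appears safe at intensities several times "higher than the FDA limit for diagnostic ultrasound (720" mW/cm²).
- Procedures for Minimizing Risks makes the commitment: "We plan to keep the LIFUP's intensity strictly under the FDA limit for diagnostic ultrasound". It gives no number there and points to an FDA guidance page.

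The documents do not state the averaging window for Ispta, the acoustic impedance, or whether the 0.71 MPa is derated.

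**The concern.** Staying below the diagnostic limit is the plan's explicit safeguard on ultrasound exposure, offered to healthy volunteers who are sonicated under propofol. Someone who reads only the risk section would expect a planned value below the limit. The methods section specifies a value equal to it. Delivering the protocol exactly as written would therefore depart from the commitment in the same protocol.

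The point is one of internal consistency in a safety statement. It does not affect any endpoint, estimate or planned analysis.

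**Working it through.** **Main check: no assumption beyond reading both 720s as the same quantity**

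- Planned intensity (LIFUP Method): 720 mW/cm², derated Ispta.
- Limit (Human Studies and Safety Profile): 720 mW/cm².
- Commitment (Procedures for Minimizing Risks): planned < limit.
- Planned − limit = 720 − 720 = 0. The strict inequality fails.

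**Side check: do the other acoustic figures reproduce 720?**

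Inputs from LIFUP Method: p = 0.71 MPa, pulse repetition frequency 100 Hz, pulse width 0.5 ms, 30 s on/30 s off. The impedance Z is not in the documents; 1.48 to 1.70 MRayl is assumed.

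1. Duty cycle within a sonication = 100 × 0.0005 = 0.05.
2. Starting from the plan's figure, an Ispta of 720 mW/cm² implies a pulse-average intensity (Isppa) of 0.720/0.05 = 14.4 W/cm². With p = √(2 × Z × Isppa), that is 0.653 MPa at Z = 1.48 and 0.700 MPa at Z = 1.70, against the stated 0.71 MPa.
3. Starting from the pressure, the plane-wave relation gives Isppa = p²/(2Z), and Ispta = Isppa × 0.05. Example at Z = 1.50 MRayl: (0.71 × 10⁶)²/(2 × 1.50 × 10⁶) = 168,033 W/m² = 16.80 W/cm², and × 0.05 gives 840 mW/cm².
4. Averaging in one pause per sonication multiplies by 30/60 = 0.5.

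| Z (MRayl) | Isppa (W/cm²) | Ispta within sonication (mW/cm²) | Relative to 720 | Ispta over on/off cycle (mW/cm²) |
|---|---|---|---|---|
| 1.48 | 17.03 | 851.5 | +18% | 425.8 |
| 1.50 | 16.80 | 840.2 | +17% | 420.1 |
| 1.63 | 15.46 | 773.2 | +7% | 386.6 |
| 1.70 | 14.83 | 741.3 | +3% | 370.7 |
| 1.75 (outside the assumed range) | 14.40 | 720.1 | 0% | 360.1 |

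5. Rounding of the pressure: 0.705 MPa at Z = 1.70 gives 731 mW/cm², which is 1.5% above 720 (731/720 = 1.015).
6. Derating: if the 0.71 MPa is not derated, the comparable value is lower. A reduction in intensity of 1 − 720/741.3 = 3% (Z = 1.70) to 1 − 720/851.5 = 15% (Z = 1.48) would bring the within-sonication value to 720, and any larger reduction would put it below.

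Over the assumed impedance range and on a common pressure basis, neither averaging window returns 720. The within-sonication window gives 3% to 18% more. The on/off window gives 41% to 48.5% less (1 − 425.8/720 and 1 − 370.7/720).

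**The case against.** The strongest reply to the main point is that the conflict is only one of wording. The commitment carries no number of its own and refers to an FDA source outside the documents. The background section quotes 720 without calling it derated or Ispta. One could also suppose that the limit is meant over a longer averaging window, on which 720 within a sonication would become 720 × 0.5 = 360. The documents do not say any of this. They give one value for the limit, in the same unit as the planned intensity, and nothing elsewhere separates the two.

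The plan also offers context that limits the weight of the point: FDA's nonsignificant-risk determination, the statement that higher intensities appear safe, and pilot experiments without propofol. That context stands, but none of it makes the commitment true as written.

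Two stronger readings are tempting, and the documents do not support either.

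- A reader might infer from 0.71 MPa and the 5% duty cycle that the exposure exceeds the limit. That needs an assumed impedance, averaging within the sonication, and a pressure on the same derated basis as the 720. The documents state none of these. Averaging within a sonication is the more natural reading, because the 720 is attached to sonications of 30 s each, but it remains an inference. At the upper end of the assumed impedance range the gap is 0.70 against 0.71 MPa, which is small for a figure that the plan calls estimated.
- A reader might infer that staff cannot tell which figure governs the device setting. LIFUP Method gives the only operating intensity. The other sections give background and a ceiling, and 0.71 MPa is an estimated result at the target.

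**Conclusion.** The contradiction holds on the plan's own figures. The planned intensity equals the stated limit, the difference is zero, and the commitment is to be strictly below. This rests only on taking both 720 mW/cm² figures as the same quantity, which is how the plan presents them.

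The pressure check is a side note. Under the stated assumptions the figures give about 741 to 851 mW/cm² within a sonication, or about 371 to 426 over the on/off cycle. The supportable conclusion is that the plan's acoustic figures cannot be verified against each other until their basis is stated. It does not follow that the limit is exceeded or that the exposure is unsafe.

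The correction should be made because the statement is a safety commitment that is wrong as written and cheap to put right.

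**What to change.** Reconcile LIFUP Method, Human Studies and Safety Profile related to LIFUP, and Procedures for Minimizing Risks so that the planned intensity and the commitment relative to the limit are both true. Give the limit as a number, with its quantity, next to the commitment.

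In the same edit, put Ispta, peak pressure, duty cycle and the limit on one stated basis (derated or not, averaging window, assumed impedance), and confirm that the figures agree on it. Which exposure is right is for the investigators and the device manufacturer; none is proposed here.

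The cost is a short recalculation and wording changes in two or three places, possibly with a notification to the IRB. The design, sample size and analysis do not change.

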#### **Adverse Events**

Adverse events will be monitored throughout the procedures and for 24 hours after the procedure via a phone call to the subjects. We will follow their medical record for 30 days following the procedure. Complications or adverse events that are observed by the investigator or reported by the subject will be recorded. For all adverse events and complications, a description of the event, date first observed, any action taken and ultimate outcome will be recorded.

For all adverse events, sufficient information will be pursued and/or obtained as to permit 1) an adequate determination of the outcome of the event (i.e. whether the event should be classified as a serious adverse event) and; 2) an assessment of the causal relationship between the adverse event and the investigational device, or if applicable, the other study treatments of diagnostic product(s). Adverse events felt to be associated with the investigational device, or if applicable, other study treatment or diagnostic product(s) will be followed until the event (or it sequelae) or the abnormal test finding resolves or stabilizes at a level acceptable to the sponsor-investigator. Adverse events will be reported to the IRB according to their reporting guidelines.

# **Serious and Unanticipated Adverse Device Events**

An unanticipated adverse device event is defined as "any serious adverse effect on health or safety or any life-threatening problem or death caused by, or associated with, a device if that effect, problem, or death was not previously identified in nature, severity, or degree of incidence in the investigational plan, or any other unanticipated serious problem associated with a device that relates to the rights, safety or welfare of subjects.

The sponsor-investigator will promptly review documented adverse events and abnormal test findings to determine 1) if the abnormal test finding should be classified as an adverse event; 2) if there is a reasonable possibility that the adverse event was caused by the investigational device or, if applicable, other study treatment of diagnostic products(s) and 3) if the adverse event meets the criteria for a serious adverse event. The sponsor shall promptly report the results of an evaluation of any serious and unanticipated adverse event to the FDA, the University of Michigan IRBMED and participating investigators (if any) as soon as possible, but not later than 10 working days after the sponsor first receives notice of the effect.

## Confidentiality

Strict subject confidentiality will be maintained. Subjects will be assigned a code number following their first contact in the protocol. This number will be used throughout the experiment and will be the only identifier on behavioral and physiological archival data, and magnetic resonance (MR) scans. The identity of subjects will not be revealed at scientific meetings, in publications or other vehicles of public communication. Data will be pooled across subjects where appropriate. Only the PIs, Co-investigators, and the study coordinator will have access to the ID code, which will be stored in a locked file separate from the data.

Any behavioral data collected on the subjects will be coded by study ID numbers and entered directly into notebook computers used in the field. These computers are password protected and stored behind a locked door when not in use. Clinical and biographic data are entered into the database using the ID number only. Only select staff members have access to the actual paper copies. Medical information will be released by name only to health care providers, and then only with written permission from the subject.

